8.3. Analysis Methods

8.3.1. Primary Efficacy Analyses

The primary endpoint is the change from baseline to Week 16 in SNOT-22 total score.

SNOT-22 is a validated questionnaire to assess the impact of CRS on quality of life (QOL) and utilizes a 2-week recall period. It is a 22-item outcome measure on a 5-point category scale applicable to sinonasal conditions and surgical treatments. The questionnaire consists of 22 items across 5 domains: Nasal, Ear, Sleep, General and Practical, and Emotional. A scale ranging from 0 (no problem) to 5 (problem as bad as it can be) is used to respond to each item in the questionnaire. The total scores range from 0 to 110 with higher total scores implying greater impact of CRS on QOL. A Minimal Clinically Important Difference (MCID) is available: 8.90 ([Hopkins, 2009](#)).

Total and domain scores will be derived by taking the sum of the non-missing item responses at each visit.

If the number of subjects overall with a missing change from baseline to Week 16 SNOT-22 total score is < 10%:

- The primary analysis will be mixed-effects model with repeated measures (MMRM) without multiple imputation (MI).
- As a sensitivity analysis, analysis of covariance (ANCOVA) without MI will also be performed.

If the number of subjects overall with a missing change from baseline to Week 16 SNOT-22 total score is $\geq 10\%$:

- The primary analysis will be MMRM with MI.
- As sensitivity analyses, MMRM without MI and ANCOVA with MI will also be performed.

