telithromycin	Ketek
tofisopam	Emandaxin, Grandaxin

Table 10: Prohibited Food and Herbal Supplements Associated with CYP3A4 Induction or Inhibition

Name	Brand Names	Notes/Description
Grapefruit /Grapefruit juice		Includes sodas that contain concentrated grapefruit juice
Marmalade		
Seville/blood oranges		
St. John's Wort		
Curcumin		

10.11. Appendix 11: Guidance to Address a Pandemic or Other Global Health Emergencies and Potential Impact on the Clinical Study

In the occurrence of a global health pandemic affecting the conduct of the ongoing study, such as the COVID-19 pandemic, study conduct may be adjusted due to subjects being in self-isolation/quarantine, limited access to public places (including hospitals) due to the risk of spreading infections, and health care professionals being committed to critical tasks (FDA, 2020; EMA, 2020; Health Canada, 2020; MHRA, 2020).

Adjustments to the GB001-2101 protocol may be made as described below, in line with global regulatory authorities guidance in order to ensure the safety of study participants, maintain compliance with GCP, and minimize the risks to trial integrity during the COVID-19 pandemic (FDA, 2020; EMA, 2020; Health Canada, 2020; MHRA, 2020). Member states within the National Competent Authorities may issue their own guidance requiring country specific recommendations to be followed.

- In the case of missed visits due to COVID-19 (or other health pandemic) related reasons:
 - The site should make every effort to contact the subject to confirm and document the reason for the missed visit, and at minimum evaluate AEs/SAEs, concomitant medications, and the SNOT-22 questionnaire in order to assess subject status.
 - The subject should continue to collect the daily morning and evening symptom diary as described in [Section 8.1.4](#).
- Alternative methods of collecting study assessments may be considered where possible:
 - Questionnaires, including SNOT-22, UPSIT, and ACQ-5, may be self-administered by the subject at home.
 - In certain situations, with Sponsor approval, a local laboratory may be used.
- Alternative methods of supplying IP to study subjects (eg, direct-to-patient shipment from site) may be considered where possible.

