8.3.1.2. MMRM with MI

Missing SNOT-22 total scores at post-baseline visits will be imputed using an MI approach. Missing SNOT-22 total scores at baseline will not be imputed.

The following steps will be performed:

- Step 1: Intermittent missing values will be imputed using the Markov Chain Monte Carlo (MCMC) method ([Schafer, 1997](#)), using a noninformative prior (Jeffreys) for the prior information for the means and covariances and expectation-maximization (EM) for the initial mean and covariance estimates.
- Step 2: Monotone missing values will then be imputed using a linear regression model ([Allison, 2005](#)) including the imputed intermittent missing values in step 1. A monotone missing pattern is such that in the event that a variable is missing it is implied that all subsequent variables are also missing (e.g., once a subject withdraws from study, no additional data is expected for that subject).
- For each step, MI will be performed within each treatment group with covariates for disease status stratification factor values used for randomization (CRSwNP with

comorbid asthma, CRSwNP without comorbid asthma, and CRSsNP), region (United States, Eastern Europe), and non-missing values for baseline SNOT-22 total score and Weeks 4, 8, 12, and 16 SNOT-22 total scores. Should convergence issues occur due to small cell size for the categorical covariates at either step, the categorical variable(s) causing convergence issues will be removed from the model.

- Missing change from baseline and percent change from baseline in SNOT-22 total scores will be computed from the imputed SNOT-22 total scores.
- The analysis of the primary endpoint as described in [Section 8.3.1](#) will be performed for each complete, imputed dataset.
- For step 1, fifty imputations will be performed. For step 2, 1 imputation will be performed if 50 imputations were performed for step 1. Fifty imputations will be performed for step 2 if step 1 was skipped (e.g., for assessments only collected once post-baseline or for endpoints without intermittent missing values).
- Results of the MMRM on the multiple imputed data sets will be combined to generate an overall estimate and associated variance using Rubin's rules ([Rubin, 1987](#)).

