8.3.2.1. Change from Baseline to Week 16 Endpoints

8.3.2.1.1. Lund-Mackay and UPSIT Scores

Lund-Mackay scores are based on the centralized imaging data assessments and scored by blinded central reading at the imaging core laboratory. The Lund-Mackay system is based on localization with points given for degree of opacification: 0 = normal, 1 = partial opacification, 2 = total opacification. These points are then applied to each sinus (maxillary, anterior ethmoid, posterior ethmoid, sphenoid, and frontal sinus) on each side. The osteomeatal complex on each side is graded as 0 = not occluded, or 2 = occluded, deriving a maximum score of 12 per side, for a total score ranging from 0 to 24 ([Lund, 1993](#)). Of note, an aplastic (absent) frontal sinus receives a score of 0.

The UPSIT test consists of four booklets, each containing 10 odorants with one odorant per page ([Doty, 1984](#)). The test-time is about 15 minutes. The stimuli are embedded in 10–50 μm diameter plastic microcapsules on brown strips at the bottom of each page. Above each odorant strip is a multiple-choice question with four alternative words to describe the odor. The subject is asked to release the odorant by rubbing the brown-strip with the tip of a pencil and to indicate which of four words best describes the odor. An UPSIT score will only be derived if all 40 responses are non-missing. A higher UPSIT score indicates better olfaction. Anosmia categories for the UPSIT score are defined as:

- Anosmia = 0 - 18
- Severe Microsmia = 19 – 25
- Moderate Microsmia = 26 - 30
- Mild Microsmia = 31 – 34

- Normal = 35 – 40

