8.3.3.5.2. ACQ-5 Score

The ACQ-5 is a five-item questionnaire which has been developed as a measure of the subject's asthma control that can be quickly and easily completed (Juniper, 2005). The response options for each of these questions consists of a zero (no impairment/limitation) to 6 (total impairment/limitation) scale with the total score ranging from 0 to 30. ACQ-5 score is the average of the 5 non-missing items and will be calculated at each visit for each subject. The MCID is 0.5 points. ACQ-5 will be conducted only in subjects who reported a diagnosis of asthma at the Screening visit.

Change from baseline to Week 16 in ACQ-5 score will be analyzed using an ANCOVA model without MI. The ANCOVA model will be analogous to the model described in [Section 8.3.1.3](#),

and will include covariates for treatment group, region (United States, Eastern Europe), and baseline ACQ-5 score. Actual and change from baseline values in ACQ-5 score will be descriptively summarized by visit using as observed data.

ACQ-5 scores will also be presented in a by-subject data listing.

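### The SNOT-22 total sums only the answered items, so each skipped item is scored 0, the best value, and the partial total counts as observed in the primary analysis

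*SAP*

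**What the plan says.** SAP Section 8.3.1 gives the item scale as follows: "A scale ranging from 0 (no problem) to 5 (problem as bad as it can be) is used to respond to each item". On the total it says: "The total scores range from 0 to 110 with higher total scores implying greater impact of CRS on QOL". The scoring rule is: "Total and domain scores will be derived by taking the sum of the non-missing item responses at each visit". Neither that section, SAP Sections 8.3.1.1 to 8.3.1.5, nor Protocol Section 8.1.1 and Appendix 9 set a minimum number of answered items, a proration, or a condition under which an incomplete form gives a missing total.

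The missing-data provisions act on totals only. The 10% threshold in SAP Section 8.3.1 counts subjects without a Week 16 change in total score. SAP Section 8.3.1.2 says: "Missing SNOT-22 total scores at post-baseline visits will be imputed using an MI approach".

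The other multi-item measures are scored differently. For UPSIT (SAP Section 8.3.2.1.1): "An UPSIT score will only be derived if all 40 responses are non-missing". For ACQ-5 (SAP Section 8.3.3.5.2): "ACQ-5 score is the average of the 5 non-missing items and will be calculated at each visit for each subject". Post-baseline diary symptom scores need at least half of the entries over the prior 4 weeks (SAP Section 8.3.2.1.2).

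SNOT-22 is normally completed at clinic visits, but the pandemic guidance in Protocol Appendix 11 (Section 10.11) adds: "Questionnaires, including SNOT-22, UPSIT, and ACQ-5, may be self-administered by the subject at home".

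**The concern.** Summing only the answered items is arithmetically the same as imputing 0 for each blank, and 0 is the most favourable answer. A form with m answers cannot exceed 5m points, so a change from baseline can subtract totals that sit on different ranges.

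Nothing planned would reveal this. A partial form has a total, so it passes the 10% check as observed and is left alone by the imputation. MMRM without MI and both ANCOVA versions reuse the same totals. So do the baseline covariate, the responder endpoint (a decrease of at least 9 points) and the subgroup analyses. Under the UPSIT, ACQ-5 and diary rules a blank is never scored as 0; the primary endpoint is the exception, and no reason is given.

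At stake are individual changes and responder classifications, and the between-arm difference if skipping, or the severity of the skipped items, differs by arm. If skipping is equal, the rule mainly adds noise and slightly shrinks a true effect.

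**Working it through.** **Inputs from the documents.** 22 items scored 0 to 5 and MCID 8.90 (SAP Section 8.3.1); responder cut of 9 points (SAP Section 8.3.1.5); difference 12.0, SD 16.8, two-sided alpha 0.050, 50 per arm, dropout 15% (SAP Section 2.5).

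**Assumptions.** The documents give no rate of skipped items and no expected mean score. I take a mean item score of 2 (total 44), k = 1, 2, 5 or 11 items skipped, and 10% of forms affected. Skipping occurs at Week 16 only.

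**The plan's own figure.** Evaluable n = 50 × 0.85 = 42.5 per arm. SE = 16.8 × √(2/42.5) = 3.644. Noncentrality = 12.0/3.644 = 3.293. The noncentral t with 83 df gives power 90.2%, which agrees with the stated 90%.

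**One subject.** Error in the Week 16 total = −k × 2, that is −2, −4, −10 or −22 points for k = 1, 2, 5 or 11. Two items can move the change by up to 2 × 5 = 10 points if both were truly 5. Three items truly at 3 turn no change into −9, a false responder. The same skips at baseline give errors of the opposite sign.

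**Unequal skipping: 10% more incomplete forms in one arm.** Shift in the difference = 0.10 × k × 2. Power uses an effect of 12.0 minus the shift; type I error uses a true effect of 0 with the shift added.

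| k | Shift (points) | Share of 12.0 | Power if against GB001 | Two-sided type I error |
|---|---|---|---|---|
| 1 | 0.2 | 1.7% | 89.3% | 5.0% |
| 2 | 0.4 | 3.3% | 88.2% | 5.1% |
| 5 | 1.0 | 8.3% | 84.7% | 5.8% |
| 11 | 2.2 | 18.3% | 75.7% | 9.2% |

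**Equal skipping: 10% of forms in both arms, true effect 12.0.** Skipped items carry k/22 of the effect, so the loss = 0.10 × (k/22) × 12. The SD becomes √(16.8² + 0.10 × 0.90 × (k × 1.73)²), where 1.73 = 38/22 and 38 is the average of totals 44 and 32.

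| k | Loss (points) | SD | Power |
|---|---|---|---|
| 1 | 0.05 | 16.81 | 89.9% |
| 2 | 0.11 | 16.83 | 89.6% |
| 5 | 0.27 | 17.00 | 88.2% |
| 11 | 0.60 | 17.74 | 83.3% |

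**Effect on the 10% trigger.** Counting partial forms as observed lowers the apparent missingness, but the planned 15% dropout would already exceed 10% and make MMRM with MI the primary analysis. This effect is secondary.

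**The case against.** The strongest reply is that nothing shows the problem occurs. The documents do not say how often items are skipped or whether the capture method blocks skipping; if it does, the effect is nil. Every size above rests on assumed rates. The ordinary case of 1 to 2 skipped items is small on these figures. The large ones need about 4 more half-blank forms in one arm than in the other (0.10 × 42.5), and in a double-blind trial there is no evident reason for skipping to differ by arm. These points stand, and they limit the severity.

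Three narrower points also stand in part:

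- An item skipped at both visits drops out of the change. There is no error if it did not change, and improvement is understated if it improved: with every item going from 3 to 2 and two items skipped at both visits, the change is −20 instead of −22.
- The entry rules (SNOT-22 below 20 excluded at screening, at least 17 required at randomization) make a nearly blank baseline form unlikely, since 17 points need at least 4 answered items. They do not stop a few skipped items.
- SAP Section 3.3 lists a possible subgroup analysis by alternative collection method, including SNOT-22 at home. It is conditional and would not repair the scoring.

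The ACQ-5 wording could also mean that all five items must be present. On either reading a blank is not scored 0, so the contrast holds. None of this alters the fact that the SAP states a rule, and that the rule gives a wrong score whenever a skipped item was not truly 0, unless the item was skipped at both visits and did not change.

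**Conclusion.** The concern holds. It is a stated scoring rule that misscores incomplete forms, not merely a missing detail, and no planned sensitivity analysis would detect it. It should be fixed, but it is not a fatal flaw, and confidence in its practical importance is medium.

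Its trial-level size cannot be known from the documents. Under the assumptions above, the 1 to 2 item case costs at most about 2 percentage points of power (90.2% to 88.2%) and leaves type I error at 5.0% to 5.1%. Only heavily incomplete forms concentrated in one arm matter materially: at 11 skipped items, power is 75.7% or type I error 9.2%. For a single subject the effect can be large, because five skipped items of average score 2 exceed both the MCID and the responder cut. The sample-size calculation itself is unaffected.

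**What to change.** In SAP Section 8.3.1, replace the scoring sentence with a rule of this kind: if at least 11 of the 22 items are answered, the total is 22 times the mean of the answered items; otherwise the total is missing and is handled by the MMRM or MI already planned. Apply the same half-rule to each domain score and to baseline, before the 10% missingness check. Tabulate SNOT-22 item completeness by visit on blinded data, and keep the plain-sum total as a sensitivity analysis. The half threshold is a choice that parallels the SAP's own diary rule; requiring all items, as for UPSIT, would also close the gap but would lose more totals.

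The cost is one SAP sentence, a few lines of code, one blinded table and one extra run. A few totals may become missing. Proration assumes that skipped items resemble the answered ones, which may not hold across nasal, ear, sleep and emotional items; comparison with the plain-sum analysis shows whether the choice matters. If all forms are complete, no result changes.

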8.3.1.1. MMRM without MI

MMRM will be performed using a restricted maximum-likelihood (REML)-based approach. The MMRM model will include change from baseline scores through Week 16 as the response variable; the fixed, categorical covariates of treatment group, disease status stratification factor values used for randomization (CRSwNP with comorbid asthma, CRSwNP without comorbid asthma, and CRSsNP), region (United States, Eastern Europe), visit, and treatment group by visit interaction; and the continuous, fixed covariates of baseline SNOT-22 total score and baseline SNOT-22 total score by visit interaction. An unstructured covariance structure will be used to model within-subject error.

If the analysis fails to converge due to the complexity of model specification, the following will be considered to enable model convergence: 1) use of maximum likelihood estimation instead of REML; and/or 2) a compound symmetric or first-order autoregressive covariance structure will

be utilized, based on the covariance structure converging to better fit as determined based on Akaike's information criterion ([Akaike, 1973](#)); and/or 3) reduced models. In the case of 3), if the full model does not converge after using maximum likelihood estimation or different covariance structures, reduced models will be fit using REML and an unstructured covariance structure. The reduced model will include treatment group, visit, and treatment group by visit interaction.

Parameters will be estimated using REML with the Newton-Raphson algorithm. Treatment comparisons will be derived from the MMRM. The number and percent of subjects contributing to the MMRM analysis and descriptive statistics along with the LS means, SEs, and corresponding 95% CIs for each treatment group will be provided. The difference in LS means, SE, corresponding 95% CI, and p-value with Kenward-Roger adjustment ([Kenward, 1997](#)) will also be provided for comparison for the GB001 40 mg group versus placebo. Results will be presented for the total score only, for change from baseline to Week 16 and separately for change from baseline to all visits through Week 16 (excluding descriptive statistics).

A bar graph of the LS mean change from baseline to Week 16 by treatment group, including 95% CIs, for the total score will be provided. A figure of LS mean change from baseline in the total score, including 95% CIs, by visit will also be provided. The figures reporting model-based results will use the primary analysis approach based on the amount of missing data as described in [Table 1](#). Lastly, a bar graph of the mean change from baseline to Week 16 by treatment group, including SE bars, for each domain score will be provided using as observed data.

Actual, change from baseline, and percent change from baseline values in total and domain scores will be descriptively summarized by visit using as observed data.

SNOT-22 total and domain scores will also be presented in a by-subject data listing.

8.3.1.2. MMRM with MI

Missing SNOT-22 total scores at post-baseline visits will be imputed using an MI approach. Missing SNOT-22 total scores at baseline will not be imputed.

The following steps will be performed:

- Step 1: Intermittent missing values will be imputed using the Markov Chain Monte Carlo (MCMC) method ([Schafer, 1997](#)), using a noninformative prior (Jeffreys) for the prior information for the means and covariances and expectation-maximization (EM) for the initial mean and covariance estimates.
- Step 2: Monotone missing values will then be imputed using a linear regression model ([Allison, 2005](#)) including the imputed intermittent missing values in step 1. A monotone missing pattern is such that in the event that a variable is missing it is implied that all subsequent variables are also missing (e.g., once a subject withdraws from study, no additional data is expected for that subject).
- For each step, MI will be performed within each treatment group with covariates for disease status stratification factor values used for randomization (CRSwNP with

comorbid asthma, CRSwNP without comorbid asthma, and CRSsNP), region (United States, Eastern Europe), and non-missing values for baseline SNOT-22 total score and Weeks 4, 8, 12, and 16 SNOT-22 total scores. Should convergence issues occur due to small cell size for the categorical covariates at either step, the categorical variable(s) causing convergence issues will be removed from the model.

- Missing change from baseline and percent change from baseline in SNOT-22 total scores will be computed from the imputed SNOT-22 total scores.
- The analysis of the primary endpoint as described in [Section 8.3.1](#) will be performed for each complete, imputed dataset.
- For step 1, fifty imputations will be performed. For step 2, 1 imputation will be performed if 50 imputations were performed for step 1. Fifty imputations will be performed for step 2 if step 1 was skipped (e.g., for assessments only collected once post-baseline or for endpoints without intermittent missing values).
- Results of the MMRM on the multiple imputed data sets will be combined to generate an overall estimate and associated variance using Rubin's rules ([Rubin, 1987](#)).

Results will be presented as described in [Section 8.3.1.1](#) but using the MI data and the number and percent of subjects with an MI value or an observed value for each treatment group will also be provided. In addition, actual, change from baseline, and percent change from baseline values in total and domain scores will be descriptively summarized by visit using MI data.

8.3.1.3. ANCOVA without MI

For ANCOVA without MI, the models will include covariates for treatment group, disease status stratification factor values used for randomization (CRSwNP with comorbid asthma, CRSwNP without comorbid asthma, and CRSsNP), region (United States, Eastern Europe), and baseline SNOT-22 total score.

Descriptive statistics for change from baseline to Week 16 along with the LS means, SEs, and corresponding 95% CIs for each treatment group will be provided. The difference in LS means, SE, corresponding 95% CI, and p-value for the GB001 40 mg group versus placebo will also be constructed from the ANCOVA model. Results will be presented for the total score only.

8.3.1.4. ANCOVA with MI

The imputed data described in [Section 8.3.1.2](#) will be used for the ANCOVA with MI analyses. Covariate adjustment will be the same as in [Section 8.3.1.3](#).

Results will be presented as described in [Section 8.3.1.3](#) but using the MI data.

8.3.1.5. Additional Analyses of the Primary Endpoint

The proportion of subjects with a ≥ 9 point decrease from baseline at Week 16 in SNOT-22 total score will be analyzed in the subset of the ITT population who have a non-missing baseline and at least one post-baseline value. Logistic regression modeling will be used to compare the

GB001 40 mg group with placebo using as observed data with covariates for treatment group, disease status stratification factor values used for randomization (CRSwNP with comorbid asthma, CRSwNP without comorbid asthma, and CRSsNP), region (United States, Eastern Europe), and baseline SNOT-22 total score.

The number and proportion of subjects with a ≥ 9 point decrease from baseline at Week 16 in SNOT-22 total score and corresponding 95% Wilson (Score) CIs ([Wilson, 1927](#)) will be summarized by treatment group. The OR, corresponding asymptotic 95% CI along with the absolute difference in proportions and corresponding 95% CI, and p-value will be summarized for the GB001 40 mg group versus placebo. The 95% CI for the absolute difference will be Newcombe continuity-corrected CI ([Newcombe, 1998](#)). The percentage reduction in odds and corresponding 95% CI will also be provided.

The number and proportion of subjects with a ≥ 9 point decrease from baseline in SNOT-22 total score will also be summarized by visit as described above at Week 16.

